10.2.2 Organ Response Criteria

Cardiac:

Cardiac response:

- NT-proBNP response (>30% and >300 ng/L decrease in patients with a baseline NT-proBNP >650 ng/L)
- NYHA class response (> two-class decrease if baseline NYHA class 3 or 4)

Cardiac progression:

- NT-proBNP progression (>30% and >300 ng/L increase)
- cTn progression (> 33%)
- EF progression (\geq 10% decrease)

Renal:

Renal response:

- Decrease in proteinuria by > 30% or below 0.5 g/24 h without renal progression. Serum creatinine and creatinine clearance (or calculated estimated GFR) must not worsen by 25% over baseline

Renal progression:

- 50% increase (at least 1 g/day) of 24-hour urine protein to >1g/day or 25% worsening of serum creatinine or creatinine clearance

10.4 Performance Status: Patients will be graded according to the ECOG performance status scale.

POINT

DESCRIPTION

0	Fully active, able to carry on all pre-disease performance without restriction.
1	Restricted in physically strenuous activity but ambulatory and able to carry out work of a light or sedentary nature, e.g., light housework, office work.
2	Ambulatory and capable of self-care but unable to carry out any work activities; up and about more than 50% of waking hours.

- 3 Capable of limited self-care, confined to bed or chair more than 50% of waking hours.
- 4 Completely disabled; cannot carry on any self-care; totally confined to bed or chair.

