6.0 ELIGIBILITY CRITERIA

6.1 Eligibility Criteria

- Histological diagnosis of primary systemic (AL) amyloidosis:
 - a. At least one tissue demonstrating positive Congo Red staining with characteristic apple green birefringence AND/OR characteristic appearance of fibrils on electron microscopy **AND**
 - b. Evidence of a clonal plasma cell dyscrasia:
 - i. Monoclonal protein in the serum and/or urine by immunofixation electrophoresis **AND/OR**
 - ii. Abnormal serum free light chain assay **AND/OR**
 - iii. Clonal plasma cell population in the bone marrow demonstrated by immunohistochemistry, flow cytometry or in situ hybridization **AND**
 - c. Evidence of organ involvement other than carpal tunnel syndrome. Confirmation of tissue diagnosis at all sites of organ dysfunction is encouraged, but not required.
- Must have received at least one prior treatment regimen of proven efficacy in the treatment of AL amyloidosis. If prior treatment included ASCT, at least 6 months must have elapsed between ASCT and study drug.
- Must be ≥ 18 years of age.
- Must have a performance status of 0-2 by ECOG criteria (see Section 10.4)
- Must have adequate hepatic function as evidenced by serum bilirubin values < 2.0 mg/dL; ALT and/or AST $< 3 \times \text{ULN}$ (bilirubin < 3 mg/dL allowed if related to Gilbert's syndrome).
- Must have an absolute neutrophil count $\geq 1000/\text{mm}^3$, hemoglobin ≥ 7.5 g/dL, and platelet count $\geq 50 \times 10^9/\text{L}$

6.2 Exclusion Criteria:

- Renal Insufficiency (CrCL $< 20 \text{ mL/min}$), calculated by Cockcroft-Gault Equation
$$\text{CreatClear} = \text{Sex} * ((140 - \text{Age}) / (\text{SerumCreat})) * (\text{Weight} / 72)$$

*Equation parameters such as **Sex** have two or more discrete values that may be used in the calculation. The numbers in the parentheses, e.g. (1), represent the values that will be used.*

The default unit of measure for weight is kilograms. Please verify that the correct unit of measure has been selected.

<http://reference.medscape.com/calculator/creatinine-clearance-cockcroft-gault>
- Mayo clinic cardiac biomarker stage IIIb (see appendix 14.3)
- Evidence of significant cardiovascular conditions as specified below:
 - NT-ProBNP > 8500 ng/L (Mayo Stage IIIb patients are excluded)

- New York Heart Association (NYHA) classification IIIB or IV heart failure (see Section 10.5)

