10.0 CRITERIA FOR EVALUATION AND ENDPOINT DEFINITIONS

Patients will not be required to have a delta FLC of 40 mg/L for study entry as primary endpoint of the study is to evaluate safety and tolerability of the study drug. Hematologic responses will be assessed by other hematologic measures of disease including M-spike and presence of clonal plasma cells in the bone marrow. Organ responses will be assessed by changes in 24 hour protein excretion for patients with renal involvement; by changes in NT-proBNP for patients with cardiac involvement; and by changes in alkaline phosphatase levels and liver span for patients with hepatic involvement.

10.1 Toxicities:

Safety of the study drug will be assessed by using vital sign information in addition to data pertaining to the duration of therapy, interruption of therapy, routine laboratory assessments, and frequency and severity of AEs

10.2 Responses:

It is important to note that daratumumab is an IgGk monoclonal antibody that can be detected as an individual monoclonal band on SPEP and serum immunofixation electrophoresis (IFE). It can be confused with the endogenous IgG-k M-protein of the patient during IFE interpretation. Co-migration can introduce a bias in M-protein quantification and can also mask clearance of the patient's M-protein by IFE. For optimal M-spike monitoring, our laboratory specialist will be informed if a patient is receiving daratumumab.

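### Renal response has no baseline proteinuria condition, so a renal patient entering below 0.5 g/24 h can count as a responder after no fall or a trivial one, depending on how the 0.5 g limb is read

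*Combined protocol and SAP*

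**What the plan says.** Section 10.2.2 gives renal response two alternative limbs: "Decrease in proteinuria by > 30% or below 0.5 g/24 h without renal progression". It adds a renal-function condition: "Serum creatinine and creatinine clearance (or calculated estimated GFR) must not worsen by 25% over baseline". Renal progression is "50% increase (at least 1 g/day) of 24-hour urine protein to >1g/day or 25% worsening of serum creatinine or creatinine clearance".

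On who is assessed, Section 10.0 says "Organ responses will be assessed by changes in 24 hour protein excretion for patients with renal involvement". No section says what makes a patient renally involved. Section 6.1 asks for "Evidence of organ involvement other than carpal tunnel syndrome" and gives no proteinuria threshold. It also says that patients "Must have received at least one prior treatment regimen of proven efficacy in the treatment of AL amyloidosis".

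The cardiac response criteria in 10.2.2 are both conditioned on baseline. The biomarker criterion is a "decrease in patients with a baseline NT-proBNP >650 ng/L", and the NYHA criterion applies only to patients starting in class 3 or 4.

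Organ response, including proteinuria, is a secondary endpoint (Sections 1.0 and 11.3). Section 11.3 uses everyone who received a dose for efficacy, describes no renal-evaluable subset, and plans descriptive summaries without hypothesis tests.

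**The concern.** A response criterion should separate patients who improved from those who did not. The >30% limb does so by comparing follow-up with baseline. The 0.5 g limb names only an end level, and nothing in the rule requires the patient to have started above it.

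The trial enrols previously treated patients, so a patient could have recognised renal involvement and already have low proteinuria at entry. That is plausible, but the documents neither state it nor rule it out. Such a patient could satisfy the 0.5 g limb without benefit from daratumumab.

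What is at stake is the meaning of one reported rate. The trial has a single arm and about 20 evaluable patients, so there is no control group in which the same misclassification would show up, and a few patients can move the figure noticeably.

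**Working it through.** The documents give no renal response rate, number of renal patients or distribution of baseline proteinuria, so there is no planned figure to reproduce. The check applies the written rule to example values and then shows how much one patient matters.

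**Step 1: can the progression clause exclude these patients?** Progression on proteinuria needs a rise of at least 1 g/day and a level above 1 g/day. A follow-up value below 0.5 g can never meet that. A rise from 0.30 to 0.45 g is 0.15/0.30 = 50%, yet it is not progression. Only a 25% worsening of creatinine or clearance would disqualify the patient.

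**Step 2: three readings of the 0.5 g limb**, with renal function stable throughout.

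- A: any follow-up level below 0.5 g.
- B: any decrease that ends below 0.5 g.
- C: a fall from 0.5 g or more to below 0.5 g.

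| Baseline to follow-up (g/24 h) | Change | A | B | C |
|---|---|---|---|---|
| 0.40 to 0.40 | 0% | response | no | no |
| 0.40 to 0.39 | 0.01/0.40 = 2.5% fall | response | response | no |
| 0.30 to 0.45 | 50% rise | response | no | no |
| 0.55 to 0.48 | 0.07/0.55 = 12.7% fall | response | response | response |
| 3.0 to 2.0 | 1.0/3.0 = 33.3% fall | response | response | response |

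Readings A and B both admit a patient whose proteinuria has not meaningfully changed. Only C does not, and the text does not state C.

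**Step 3: weight of one patient.** With m renal patients, classing one as a responder instead of a non-responder moves the rate by 1/m. For assumed m of 10, 15 and 20 this is 10.0, 6.7 and 5.0 percentage points.

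**Step 4: direction.** Assume m = 15, a 30% response rate among those starting at 0.5 g or more, and s patients who start below 0.5 g and stay stable.

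- Reading A: (0.30 × (15 − s) + s)/15.
- Reading C, low-baseline patients kept as non-responders: 0.30 × (15 − s)/15.
- Reading C, low-baseline patients outside the denominator: 30% for any s.

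| s | A | C, kept in | C, taken out |
|---|---|---|---|
| 0 | 30.0% | 30.0% | 30.0% |
| 1 | 5.2/15 = 34.7% | 4.2/15 = 28.0% | 30.0% |
| 2 | 5.9/15 = 39.3% | 3.9/15 = 26.0% | 30.0% |
| 3 | 6.6/15 = 44.0% | 3.6/15 = 24.0% | 30.0% |

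With three such patients, the same data give 24%, 30% or 44%, depending on a choice that the plan leaves open.

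**The case against.** The strongest reply is grammatical. The sentence opens with a decrease in proteinuria, which can govern both limbs, and Section 10.0 says that organ response is judged by changes. A reader might infer that anyone below 0.5 g at entry is a responder with no change at all. The documents do not support that as a general statement, because it holds only under reading A. But the decrease reading does not rescue the rule: 0.40 to 0.39 g is still a response. Nor is the decrease reading clearly intended. The VGPR definition in 10.2.1 states explicitly that dFLC must be reduced to a level; the renal rule has no such wording.

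A reader might also infer that the rule can only inflate the rate. That fails too. Under reading C, with stable low-baseline patients kept as non-responders, the rate falls.

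Nor can the effect be sized from the documents. If a share f of renal patients start below 0.5 g and all count as responders, and the rate in the others is p, the reported rate is f + (1 − f)p. With p = 40% this is 43%, 46% and 52% for f of 5%, 10% and 20%. Both f and p are assumptions, f may be zero, and 5% of 15 patients is less than one patient. The formula also assumes that every such patient stays below 0.5 g with stable renal function.

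Sampling error is large as well: 6 responders in 15 have an exact 95% interval of about 16% to 68%. That limits the importance of the point, but an interval does not correct a classification error. The cardiac contrast alone does not prove a drafting mistake, since the biomarkers differ. It does show that the section sets baseline conditions elsewhere.

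**Conclusion.** The point holds as a defect in an endpoint definition. The renal rule lacks a baseline condition, renal involvement is undefined, and the proteinuria part of the progression clause cannot catch patients at low levels. On two of the three readings, a renal patient entering below 0.5 g/24 h with stable renal function is a responder without meaningful improvement. On the third, the patient dilutes the rate unless removed from the denominator.

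Each such patient is worth about 5 to 10 percentage points if there are 10 to 20 renal patients, an assumed range. How many will enrol is unknown and may be none, so the total effect and its direction cannot be stated.

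The consequence is confined to a secondary, descriptive rate. The primary safety endpoint, sample size and interim safety review do not depend on it. Section 7.4 uses organ progression, not organ response, so treatment decisions are not affected either. The correction is worth making because it is cheap and the rate cannot be interpreted without it.

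**What to change.** In Section 10.2.2:

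- Define the renal-response denominator as patients with renal involvement and screening 24-hour urine protein of at least 0.5 g.
- State that the 0.5 g limb requires a fall from at least 0.5 g to below 0.5 g.
- Leave the >30% limb, the renal-function condition and the progression rule as they are.
- Report the number of renal patients excluded for low baseline proteinuria.

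A sentence saying how renal involvement is established at entry would complete the definition. No new data are needed: the study calendar in Section 9.0 already collects 24-hour urine protein at screening and every three months.

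The cost is a slightly smaller denominator and possibly a less favourable rate. A patient going from 0.40 to 0.25 g (a 37.5% fall) would also leave the analysis despite meeting the >30% limb. Modest falls just above the floor, such as 0.55 to 0.48 g, would still count; the change does not address those.

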10.5 New York Heart Association (NYHA) Classification of Cardiac Disease

Class	Functional Capacity	Objective Assessment
I	Patients with cardiac disease but without resulting limitations of physical activity. Ordinary physical activity does not cause undue fatigue, palpitation, dyspnea, or anginal pain.	No objective evidence of cardiovascular disease.
II	Patients with cardiac disease resulting in slight limitation of physical activity. They are comfortable at rest. Ordinary physical activity results in fatigue, palpitation, dyspnea, or anginal pain.	Objective evidence of minimal cardiovascular disease.
III	Patients with cardiac disease resulting in marked limitation of physical activity. They are comfortable at rest. Less than ordinary activity causes fatigue, palpitation, dyspnea, or anginal pain.	Objective evidence of moderately severe cardiovascular disease.
IV	Patients with cardiac disease resulting in inability to carry on any physical activity without discomfort. Symptoms of heart failure or the anginal syndrome may be present even at rest. If any physical activity is undertaken, discomfort is increased.	Objective evidence of severe cardiovascular disease.

11.0 STATISTICAL CONSIDERATIONS

11.1 Sample Size Estimation

Estimated patient accrual and trial duration: The study will be designed as a single armed phase II trial, in which the response in 20 evaluable patients will be determined, with 25 patients enrolled to ensure that 20 are evaluable

Completion of accrual will be expected in ~2 years, with an additional year of monitoring and follow up after the last patient is enrolled.

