7.0 TREATMENT PLAN

Drug	Dose ^c	Frequency	Route of Administration
Daratumumab	16 mg/kg body weight	Weekly, weeks 1-8	IV infusion
Daratumumab	16 mg/kg body weight	Every 2 weeks, weeks 9-24 ^a	IV infusion
Daratumumab	16 mg/kg body weight	Every 4 weeks, week 25 ^b onwards, for up to 24 months of total study therapy	IV infusion

^a First dose of the every-2-week dosing schedule is given at week 9

^b First dose of the every-4-week dosing schedule is given at week 25

^c Weight from screening visit will be used for initial dosing and throughout treatment period but will be recalculated for weight change $\geq 10\%$.

Infusion rates for daratumumab administration

	Dilution volume	Initial rate (1 st hour)	Rate increment ^a	Maximum rate
First infusion	1000 mL	50 mL/hour	50 mL/hour every hour	200 mL/hour
Second infusion ^b	500 mL	50 mL/hour	50 mL/hour every hour	200 mL/hour
Subsequent infusion ^c	500 mL	100 mL/hour	50 mL/hour every hour	200 mL/hour

^a Consider incremental escalation of the infusion rate only in the absence of infusion reactions.

^b Use a dilution volume of 500 mL only if there were no Grade 1 (mild) or greater infusion reactions during the first 3 hours of the first infusion. Otherwise, continue to use a dilution volume of 1000 mL and instructions for the first infusion.

^c Use a modified initial rate for subsequent infusions (i.e. third infusion onwards) only if there were no Grade 1 (mild) or greater infusion reactions during a final infusion rate of ≥ 100 mL/hr in the first two infusions. Otherwise, continue to use instructions for the second infusion.

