9.0 STUDY CALENDAR

	Screening	Prior to each dose	Monthly (CxD1)	Every 3 Month beginning C4,D1	End of Study Treatment Visit ⁵
PHYSICAL⁹					
History & Physical Exam, including liver assessment	X		X ⁷	X	X
Height	X				
ECOG Performance Status (see 10.4)	X	X		X	X
Vital Signs & Weight		X		X	
Adverse Event Monitoring		X		X	X
SF-36 (QOL)	X			X	
LABORATORY-Serum					
Complete Blood Count with Differential	X	X		X	X
Beta-HCG ¹	X				
Chemistry including: BUN, creatinine, glucose, sodium, potassium, chloride, bicarb, cholesterol, CK, calcium, total protein, LDH, magnesium, phosphorous, triglycerides, uric acid, TSH, amylase	X	X		X	X
BUN / Serum Creatinine	X	X		X	X
Creatinine Clearance ³	X				
Hepatic Function Testing: ALT/AST, Bilirubin, Albumin, Alkaline Phosphatase	X	X		X	X
β-2 Microglobulin / C-reactive protein	X			X	X
Cardiac enzymes: BNP/ Troponin I/NT ProBNP	X	X		X	X
Serum free light chain assay	X	X ⁸		X	X
SPEP, SIFE, Immunoglobulins	X			X	X
Coombs test; IAT (anti globulin test)	X				
Coagulation profile: PTT, INR, D-dimer, Factor X	X			X	X
HBV serology testing ¹⁰	X				
HBV DNA testing ¹¹	X				X
Type And Screen and blood bank phenotype ⁶	X				
Daratumumab-specific Immunofixation (patients with Kappa disease only)	X			X	X
LABORATORY-Urine					
Urinalysis	X			X	X
24 hour urine: total protein, creatinine, kappa, and lambda	X			X	X
UPEP / UIFE / TV	X			X	X
PATHOLOGY					
BM biopsy	X ²				
Fat aspirate (if not previously done)	X				
X-RAYS AND SCANS					
ECG / CXR	X				
Echocardiogram	X			Every 6 months	
PFTs (required for chronic smokers or known COPD)	X				

1 For women of childbearing potential only.

2 Bone marrow biopsy and aspiration must have been repeated following any previous therapy > 1 cycle.

3 CreatClear = Sex * ((140 - Age) / (SerumCreat)) * (Weight / 72); Equation parameters such as Sex have two or more discrete values that may be used in the calculation. The numbers in the parentheses, e.g. (1), represent the values that will be used. The default unit of measure for weight is kilograms. Please verify that the correct unit of measure has been selected. <http://reference.medscape.com/calculator/creatinine-clearance-cockcroft-gault>

4 While on study drug or until disease progression or start of another therapy.

5 30 days following last dose (+/-) 7 days.

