11.3 Statistical Methods

The primary endpoints for the study are related to safety and tolerability of infusion of daratumumab in AL amyloidosis with respect to infusion reactions.

Secondary endpoints include hematologic response rate of single agent daratumumab, organ responses with respect to cardiac biomarkers and proteinuria, and time to next treatment.

The Health Related Quality of Life, as reported in SF-36, will be an exploratory endpoint.

Statistical analysis will be based on all eligible subjects. Safety analysis population includes all enrolled subjects who received at least one dose of study drug. The safety analysis population will be used for evaluating subject characteristics, treatment administration, safety endpoints, and efficacy analyses.

There will be no formal statistical hypothesis testing applied in this study. Descriptive summary statistics will be used throughout. Data will be summarized primarily by administration time and aggregated across the first 8 weeks and 2 weeks after.

Continuous variables will be summarized by the number of non-missing observations, mean, standard deviation (SD), median, minimum and maximum.

Categorical variables will be summarized by the number of non-missing observations, frequencies and percentages.

All analyses will be performed using SAS® (SAS Institute Inc., Cary, North Carolina, U.S.) version 9.4 or higher.

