11.3 Handling of Missing Data

Data will be analyzed as recorded in the database. No imputation of missing values will be performed unless indicated otherwise.

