12.0 DATA AND SAFETY MONITORING PLAN

Toxicity and accrual monitoring will be performed on a routine basis by the study investigators as well as the multidisciplinary members of the Amyloid Center at Boston University, which has over 40 years' experience in the treatment of AL amyloidosis. Subjects will undergo toxicity assessment, performance status assessment and laboratory tests before each dose. Response assessment will be conducted every three months. The clinical status and laboratory reports of the study participants will be reviewed routinely by treating physicians. Dose modifications/interruptions or discontinuation will be implemented according to Section 8.

In addition, a Medical Monitor will be assigned to the study. The Medical Monitor must be a qualified clinician with relevant expertise, but no direct connection with the research, whose primary responsibility is to provide independent safety monitoring in a timely fashion. The PI will submit a

report to the Medical Monitor, at a minimum of once every 6 months, including a list of all adverse events and serious adverse events (regardless of relatedness). In addition, any unanticipated problems involving risks to participants or others and participant deaths within 30 days of study intervention will be reported to the Medical Monitor within 48 hours. The Medical Monitor is expected to provide a formal, unbiased written report evaluating individual and cumulative participant safety data when making recommendations regarding continuation of the study. Although the PI is responsible for assigning causality, the medical monitor will comment on whether or not (s)he is in agreement. Medical Monitor reports will must be submitted to the PI following each review (at a minimum of once every 6 months), which the PI will, in turn, submit to the IRB. Although there is no pre-determined criteria for early termination due to toxicity, the Medical Monitor and investigators will evaluate toxicities on a continuing basis, and will terminate the study early if toxicities exceed acceptable parameters. Each individual situation will be reviewed, and response data will be considered. The study will be stopped early if it appears that the benefit no longer outweighs the risks.

12.1 Interventional IIS Janssen Scientific Affairs Requirements for Safety Data Collection and Reporting

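### The response denominator is left open (undefined 'evaluable' in 11.1, eligible and treated patients in 11.3, no rule for unassessed patients), and VGPR can be met by patients who enter below its threshold

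*Combined protocol and SAP*

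**What the plan says.** The plan describes the response denominator in three ways.

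- Section 11.1 (Sample Size Estimation) describes a single-arm trial "in which the response in 20 evaluable patients will be determined, with 25 patients enrolled to ensure that 20 are evaluable". The word 'evaluable' is not defined there or elsewhere.
- Section 11.3 (Statistical Methods) says "Statistical analysis will be based on all eligible subjects".
- The same section defines the safety population as enrolled patients with at least one dose, and then says "The safety analysis population will be used for evaluating subject characteristics, treatment administration, safety endpoints, and efficacy analyses".

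Two general rules follow: "Categorical variables will be summarized by the number of non-missing observations, frequencies and percentages" and, under Handling of Missing Data, "No imputation of missing values will be performed unless indicated otherwise". Neither says what a response percentage is divided by, or how a treated patient without the required assessment is counted.

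On timing, section 12.0 says "Response assessment will be conducted every three months".

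On VGPR, section 10.2.1 asks only that dFLC fall to below 40 mg/L, while section 10.0 does not require a dFLC of 40 mg/L for entry. Section 10.0 refers instead to M-spike and marrow plasma cells, but 10.2.1 has no PR or VGPR rule on either, and the section 9.0 calendar schedules marrow only at screening.

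**The concern.** Hematologic and organ response are the efficacy results of a small uncontrolled trial. If the divisor is not fixed, the same data can yield different rates, and the choice may be made after the results are known. Patients who die or leave before their first scheduled assessment are unlikely to be responders, so a rate among assessed patients only would tend to be too high.

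The VGPR wording is a separate weakness in the same results. A patient who enters already below the threshold can be credited with a deep response after a trivial change.

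**Working it through.** **The plan's own figure.** Twenty evaluable of 25 enrolled implies 5/25 = 20% not evaluable, and 20/(1 − 0.20) = 25. The arithmetic is consistent, but no such rate is stated, and any rate from 17% to 20% rounds up to 25 (20/0.83 = 24.1). The figure does not reveal what 'evaluable' means.

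**What each endpoint needs, and when it is collected (sections 9.0, 10.2.1 and 10.2.2).**

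- PR and VGPR use free light chains. These are drawn before each dose ("Weekly, weeks 1-8" in section 7.0) and at the end-of-treatment visit. If the pre-dose samples are used for response, almost every treated patient should have a post-baseline value.
- Renal response uses proteinuria. The calendar line "24 hour urine: total protein, creatinine, kappa, and lambda" is marked at screening, every 3 months from C4D1, and at the end-of-treatment visit 30 days after the last dose. A patient who dies before both later visits has no scheduled follow-up value. However, creatinine is drawn before each dose and a 25% worsening is renal progression, so some early losses can already be classed as non-responders.
- CR needs serum and urine immunofixation on the same sparse schedule. It is less exposed because an abnormal light chain ratio already rules CR out, and calendar footnote 8 calls for fuller panels once light chains normalize.

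**Formula.** Let N be the treated patients in the denominator, x the responders, and k the treated, unassessed non-responders. The all-treated rate is x/N, the rate with k dropped is x/(N − k), and the gap is the difference. All values of x and k, and the renal N of 12, are assumptions. N = 25 assumes that everyone enrolled is treated.

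| Endpoint | N | x | k | x/(N − k) | x/N | Gap (points) |
|---|---|---|---|---|---|---|
| Overall hematologic | 25 | 6 | 1 | 25.0% | 24.0% | 1.0 |
| Overall hematologic | 25 | 12 | 1 | 50.0% | 48.0% | 2.0 |
| Renal | 12 | 4 | 1 | 36.4% | 33.3% | 3.0 |
| Renal | 12 | 6 | 1 | 54.5% | 50.0% | 4.5 |
| Renal | 12 | 4 | 2 | 40.0% | 33.3% | 6.7 |
| Renal | 12 | 6 | 2 | 60.0% | 50.0% | 10.0 |
| CR | 25 | 2 | 2 | 8.7% | 8.0% | 0.7 |
| CR | 25 | 2 | 4 | 9.5% | 8.0% | 1.5 |
| CR | 25 | 5 | 2 | 21.7% | 20.0% | 1.7 |
| CR | 25 | 5 | 4 | 23.8% | 20.0% | 3.8 |

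With k = 0 every gap is zero.

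**How large k might be for renal response and CR.** Under exponential survival, the share dead by month 3 is 1 − 0.5^(3/median in months).

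- Median 12 months (the untreated figure in section 2.0): 15.9%, or 4.0 of 25 and 1.9 of 12.
- Median 24 months (assumed): 8.3%, or 2.1 of 25 and 1.0 of 12.
- Median 48 months (assumed): 4.2%, or 1.1 of 25 and 0.5 of 12.

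The first line is pessimistic, since these patients are treated and stage IIIb is excluded. All three lines overstate k by treating every early death as unassessed.

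**VGPR.** With 25 patients, each one credited on the threshold alone adds 1/25 = 4.0 points. From an assumed 6/25 = 24.0%, two such patients give 8/25 = 32.0%.

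**The case against.** The strongest reply is that 11.3 already answers the question. It assigns efficacy to all treated patients, while 'evaluable' appears in an accrual sentence. That is the natural reading. It names the population but does not fix the divisor: an analyst following 11.3 could still divide by non-missing observations, and the sentence on eligible patients remains unreconciled. For hematologic response, the residual stable-disease class might be read as absorbing an unassessed patient, but the text does not say so.

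A reader might infer that the plan prescribes division by 20 and so inflates response by 25/20 = 1.25. The documents do not support this. That ratio needs all 25 treated, exactly five unassessed and none of the five a responder, and nothing in the plan makes 20 the divisor.

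A reader might also infer that any exclusion overstates response. That depends on the missing definition. If 'evaluable' means measurable disease, the excluded patients could not be scored on dFLC, and counting them as non-responders would lower the rate.

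The remaining objections concern size. Pre-dose creatinine reduces the renal exposure, and early leavers may attend the end-of-treatment visit, which includes urine and immunofixation. The documents give no renal count or responder count. Section 11.3 rules out formal hypothesis testing, so no decision depends on these rates. All of this stands, and it makes the point modest. It supplies neither a counting rule nor a baseline condition for VGPR.

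**Conclusion.** The point holds as a gap in specification for secondary, descriptive endpoints. It should be corrected, but it does not threaten the primary safety objective.

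Overall hematologic response could move by about 0 to 2 points, if 0 or 1 of 25 patients is unassessed and 6 to 12 respond. Renal response could move by about 3 to 5 points with one unassessed patient among an assumed 12, and by about 7 to 10 with two, before allowing for creatinine-based progression. CR is exposed to a lesser degree: 0.7 to 3.8 points even with a high-side 2 to 4 unassessed.

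The VGPR weakness follows from the definitions alone. Its size, 4.0 points per patient in 25, depends on how many enter below 40 mg/L, which the documents do not give.

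**What to change.** Amend 11.3 and 10.2.1 as follows.

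1. For each response endpoint, use as denominator all patients with at least one dose. For organ response, restrict this to those with that organ involved at baseline and, for NT-proBNP response, a baseline above 650 ng/L. Section 10.2.2 sets no baseline proteinuria criterion, so also state how renal involvement is established.
2. Count a treated patient who lacks the post-baseline data needed for an endpoint as a non-responder for that endpoint, and list the patient as 'not assessed'. For CR the needed data include serum and urine immunofixation; for renal response, proteinuria. State that pre-dose and end-of-treatment samples count as post-baseline data.
3. Describe the 20 in 11.1 as a planning figure, define 'evaluable', and report that rate only as a sensitivity analysis. Reconcile the reference to all eligible patients with the safety population.
4. Do not score VGPR on the 40 mg/L threshold alone in a patient already below it at baseline. Show the rate with and without such patients.

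This changes wording only and collects no new data. The cost is that the reported response rate may be lower.
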